Appendix 7: Patient Asthma Control eDiary

(For illustrative purposes only)

The following information will be captured:

In the MORNING	In the EVENING
Peak expiratory flow rate	
How did you sleep last night?	
Did you have asthma symptoms upon awakening in the morning?	
Number of puffs of rescue medication during the past 12 hours	
	Peak expiratory flow rate
	Did your respiratory symptoms stop you from performing your usual daily activities?
	How severe was your shortness of breath today?
	How was your wheeze during the past 12 hours?
	How was your cough during the past 12 hours?
	Did you have Chest tightness during the past 12 hours?
	Number of puffs of rescue medication during the past 12 hours

Appendix 8: Liver Event and Laboratory Trigger Definitions and Follow-up Requirements

Table 8-1 Liver Event and Laboratory Trigger Definitions

	Definition/ threshold
LIVER LABORATORY	3 x ULN < ALT / AST ≤ 5 x ULN
TRIGGERS	1.5 x ULN < TBL \leq 2 x ULN
LIVER EVENTS	ALT or AST > 5 × ULN
	ALP > 2 × ULN (in the absence of known bone pathology)
	TBL > 2 × ULN (in the absence of known Gilbert syndrome)
	ALT or AST > 3 × ULN and INR > 1.5
	Potential Hy's Law cases (defined as ALT or AST > 3 × ULN and TBL > 2 × ULN [mainly conjugated fraction] without notable increase in ALP to > 2 × ULN)
	Any clinical event of jaundice (or equivalent term)
	ALT or AST > 3 × ULN accompanied by (general) malaise, fatigue, abdominal pain, nausea, or vomiting, or rash with eosinophilia
	Any adverse event potentially indicative of a liver toxicity*
*These events cover the follow	ving: hepatic failure, fibrosis and cirrhosis, and other liver damage-

^{*}These events cover the following: hepatic failure, fibrosis and cirrhosis, and other liver damagerelated conditions; the non-infectious hepatitis; the benign, malignant and unspecified liver neoplasms TBL: total bilirubin; ULN: upper limit of normal

Table 8-2	Follow Up Requirement	s for Liver Events and	Laboratory Triggers
-----------	-----------------------	------------------------	---------------------

		, 00
Criteria	Actions required	Follow-up monitoring
Potential Hy's Law case ^a	Discontinue the study treatment immediately Hospitalize, if clinically appropriate Establish causality Complete liver eCRF	ALT, AST, TBL, Alb, PT/INR, ALP and γGT until resolution ^c (frequency at investigator discretion)
ALT or AST		
> 8 × ULN	Discontinue the study treatment immediately Hospitalize if clinically appropriate Establish causality Complete liver eCRF	ALT, AST, TBL, Alb, PT/INR, ALP and γGT until resolution ^c (frequency at investigator discretion)
> 3 × ULN and INR > 1.5	Discontinue the study treatment immediately Hospitalize, if clinically appropriate Establish causality Complete liver eCRF	ALT, AST, TBL, Alb, PT/INR, ALP and γGT until resolution ^c (frequency at investigator discretion)
> 5 to ≤ 8 × ULN	Repeat LFT within 48 hours If elevation persists, continue follow-up monitoring	ALT, AST, TBL, Alb, PT/INR, ALP and γGT until resolution ^c (frequency at investigator discretion)

Criteria	Actions required	Follow-up monitoring
	If elevation persists for more than 2 weeks, discontinue the study drug	
	Establish causality	
	Complete liver eCRF	
> 3 × ULN	Discontinue the study treatment	ALT, AST, TBL, Alb, PT/INR, ALP
accompanied by	immediately	and γGT until resolution ^c
symptoms ^b	Hospitalize if clinically appropriate	(frequency at investigator
	Establish causality	discretion)
	Complete liver eCRF	
> 3 to ≤ 5 × ULN	Repeat LFT within the next week	Investigator discretion
(patient is	If elevation is confirmed, initiate close	Monitor LFT within 1 to 4 weeks
asymptomatic)	observation of the patient	
ALP (isolated)		
> 2 × ULN (in the absence of known	Repeat LFT within 48 hours	Investigator discretion
bone pathology)	If elevation persists, establish causality	Monitor LFT within 1 to 4 weeks or at next visit
	Complete liver eCRF	at fiest visit
TBL (isolated)		ALT ACT TRU AU DT/IND ALD
> 2 × ULN (in the absence of known	Repeat LFT within 48 hours	ALT, AST, TBL, Alb, PT/INR, ALP and γGT until resolution ^c
Gilbert syndrome)	If elevation persists, discontinue the study drug immediately	(frequency at investigator
, ,	Hospitalize if clinically appropriate	discretion)
	Establish causality	Test for hemolysis (e.g.,
	Complete liver eCRF	reticulocytes, haptoglobin,
- 4 E to 40 LII N	·	unconjugated [indirect] bilirubin)
> 1.5 to ≤ 2 × ULN (patient is	Repeat LFT within the next week If elevation is confirmed, initiate close	Investigator discretion Monitor LFT within 1 to 4 weeks or
asymptomatic)	observation of the patient	at next visit
Jaundice	Discontinue the study treatment	ALT, AST, TBL, Alb, PT/INR, ALP
danaido	immediately	and γGT until resolution ^c
	Hospitalize the patient	(frequency at investigator
	Establish causality	discretion)
	Complete liver eCRF	
Any AE potentially indicative of a	Consider study treatment interruption or discontinuation	Investigator discretion
liver toxicity*	Hospitalization if clinically appropriate	
	Establish causality	
	Complete liver eCRF	

^aElevated ALT/AST > 3 × ULN and TBL > 2 × ULN but without notable increase in ALP to > 2 × ULN ^b(General) malaise, fatigue, abdominal pain, nausea, or vomiting, or rash with eosinophilia ^cResolution is defined as an outcome of one of the following: (1) return to baseline values, (2) stable values at three subsequent monitoring visits at least 2 weeks apart, (3) remain at elevated level after a maximum of 6 months, (4) liver transplantation, and (5) death.

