6.5.4.1 Hematology

Hemoglobin, hematocrit, red blood cell count, white blood cell count with differential, and platelet count will be measured.

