6.5.4.2 Clinical chemistry

Albumin, alkaline phosphatase, aspartate aminotransferase (AST) or Serum Glutamic-Oxaloacetic Transaminase (SGOT), alanine aminotransferase (ALT) or Serum Glutamic Pyruvic Transaminase (SGPT), bilirubin, creatinine, gamma-glutamyl transferase (γ -GT), glucose, potassium, magnesium, blood urea nitrogen (BUN) and uric acid will be measured.

If the total bilirubin concentration is increased above 1.5 times the upper limit of normal range, total bilirubin should be differentiated into the direct and indirect reacting bilirubin.

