7.3 Liver safety monitoring

To ensure patient safety and enhance reliability in determining the hepatotoxic potential of an investigational drug, a standardized process for identification, monitoring and evaluation of liver events has to be followed.

The following two categories of abnormalities/AEs have to be considered during the course of the study (irrespective of whether classified/reported as (S)AE):

- Liver laboratory triggers, which will require repeated assessments of the abnormal laboratory parameter
- Liver events, which will require close observation, follow-up monitoring and completion of the standard base liver eCRF pages

Please refer to Table 8-1 in Appendix 8 for complete definitions of liver laboratory triggers and liver events.

Every liver laboratory trigger or liver event as defined in Table 8-1 in Appendix 8 should be followed up by the investigator or designated personal at the trial site as summarized below. Detailed information is outlined in Table 8-2 in Appendix 8.

For the liver laboratory trigger:

Repeating the liver function test (LFT) within the next week to confirm elevation.

These LFT repeats should be performed using the central laboratory if possible. If this is not possible, then the repeats can be performed at a local laboratory to monitor the safety of the patient. Repeats laboratory should then be performed at central laboratory as soon as possible. If a liver event is subsequently reported, any local LFTs previously conducted that are associated with this event should be reported on the Liver eCRF pages.

If the elevation is confirmed, close observation of the patient will be initiated, including consideration of treatment interruption if deemed appropriate.

For the liver events:

- Repeating the LFT to confirm elevation as appropriate
- Discontinuation of the investigational drug if appropriate
- Hospitalization of the patient if appropriate
- A causality assessment of the liver event via exclusion of alternative causes (e.g., disease, co-medications)
- An investigation of the liver event which needs to be followed until resolution.

These investigations can include serology tests, imaging and pathology assessments, hepatologist's consultancy, based on investigator's discretion. All follow-up information, and the procedures performed should be recorded on appropriate eCRF pages, including the liver event overview eCRF pages.

7.4 **Pregnancy reporting**

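### For asymptomatic ALT/AST > 3 to ≤ 5 × ULN no protocol text names PT/INR, so detecting the mandatory stop for ALT/AST > 3 × ULN with INR > 1.5 rests on a discretionary test in that band

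*Protocol*

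**What the plan says.** - **The event and its consequence.** Protocol Appendix 8, Table 8-1, includes "ALT or AST > 3 × ULN and INR > 1.5" among the liver events. The Table 8-2 row for that event requires immediate discontinuation of study treatment.
- **The lower tier.** ALT or AST > 3 to ≤ 5 × ULN alone is a laboratory trigger in Table 8-1, not an event. Section 7.3 describes this tier as "Liver laboratory triggers, which will require repeated assessments of the abnormal laboratory parameter". The action is "Repeating the liver function test (LFT) within the next week to confirm elevation", followed by close observation if the elevation is confirmed, with treatment interruption to be considered. If the central laboratory cannot be used, "the repeats can be performed at a local laboratory to monitor the safety of the patient".
- **The Table 8-2 row for the asymptomatic band.** It says "Repeat LFT within the next week", then close observation if confirmed. Its follow-up column leaves monitoring to the investigator, with an LFT in 1 to 4 weeks. PT/INR is in neither column.
- **The next row up (> 5 to ≤ 8 × ULN).** It says "Repeat LFT within 48 hours", and its follow-up list includes PT/INR.
- **The routine panels.** Section 6.5.4.1: "Hemoglobin, hematocrit, red blood cell count, white blood cell count with differential, and platelet count will be measured". The chemistry list in Section 6.5.4.2 covers the liver enzymes, albumin and bilirubin and ends "glucose, potassium, magnesium, blood urea nitrogen (BUN) and uric acid will be measured". Neither contains PT/INR.
- **The abbreviation.** LFT is expanded in the protocol only as liver function test; its components are not listed.

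**The concern.** A stopping criterion can act only if the quantity that defines it is measured. The other laboratory criteria in Table 8-1 use ALT, AST, ALP and total bilirubin, all of which are in the routine chemistry panel. INR is the exception. In an asymptomatic patient with ALT or AST > 3 to ≤ 5 × ULN and no other liver-event finding, INR is the single result that turns a trigger under observation into an event with a mandatory stop. If nobody orders it, that patient stays classed as a trigger and may continue dosing, and sites may differ in whether they find such cases. What is at stake is the safety of the individual patient and the consistency of liver-event classification.

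**Working it through.** No sample size, power or error rate is involved, so the check sets the texts side by side.

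**Step 1. Where does detection depend on someone choosing to measure INR?** The Table 8-2 rows for ALT or AST above 3 × ULN, with the jaundice row:

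| Finding | Action in Table 8-2 | PT/INR named? |
|---|---|---|
| > 3 to ≤ 5 × ULN, asymptomatic | Repeat LFT within a week; close observation if confirmed | No |
| > 3 × ULN with listed symptoms | Stop at once | Yes |
| > 3 × ULN and TBL > 2 × ULN (potential Hy's Law) | Stop at once | Yes |
| > 3 × ULN and INR > 1.5 | Stop at once | Yes, but the row is reached only when the INR is known |
| > 5 to ≤ 8 × ULN | Repeat LFT in 48 hours; stop if it persists for more than 2 weeks | Yes |
| > 8 × ULN | Stop at once | Yes |
| Jaundice | Stop at once | Yes |

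INR > 1.5 changes the action in two rows: the asymptomatic > 3 to ≤ 5 × ULN row, and the > 5 to ≤ 8 × ULN row, where it converts a conditional stop into an immediate one. In the second of these the follow-up list supplies an INR. In the first, nothing named in the row does.

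**Step 2. Does any other text supply an INR in the asymptomatic band?**

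- Routine panels (Sections 6.5.4.1 to 6.5.4.3): no PT/INR.
- Section 7.3: repeat LFT, then close observation; no PT/INR.
- Protocol outside Appendix 8, and the SAP: INR is not mentioned. The notable liver test criteria in SAP Section 6.4 use ALT, AST, bilirubin, ALP and symptoms.
- Section 11: extra safety assessments are allowed case by case, so an INR is permitted but not prompted.
- Laboratory manual: cited in Section 6.5.4 for collection, shipment and reporting. It is not available, so it may or may not add an INR.

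**Step 3. When could this affect dosing?** After the Visit 101 screen, chemistry is scheduled on Day 1 (20 minutes before and 30 minutes after the dose), at Visit 204 (Days 84 and 85) and at a treatment discontinuation visit. Visit 202 has none, and Visit 203 is a telephone call. The gap between scheduled on-treatment chemistry samples is therefore 84 − 1 = 83 days.

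- A trigger in the Day 1 sample, or in an unscheduled sample during treatment, leaves dosing still to come.
- A trigger at Visit 204 or at treatment discontinuation arises when dosing is ending. Only classification and follow-up can change.

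**Step 4. How many patients?** The documents give no rate for ALT or AST in this band or for INR > 1.5, so no count can be computed. Exclusion criterion 10 (a clinically significant laboratory abnormality at Visit 101) reduces the number with a raised value on Day 1.

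**The case against.** The strongest reply is that the tiers are deliberate: triggers are led by investigator judgement, events by mandate, and measuring INR at the lower tier is a preference about intensity. Safeguards exist as well. Interruption must be considered once the elevation is confirmed (Section 7.3). Clinically significant abnormalities are followed until normal or explained (Section 6.5.4). The investigator should stop treatment judged detrimental (Section 5.6.2). Symptoms, jaundice or TBL > 2 × ULN move the patient to a row that names PT/INR. All of this stands, and it limits the consequence. It does not remove the mismatch, because the plan makes this combination a mandatory stop and states in Section 7.3 that liver events are to be identified by a standardized process.

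The reply on LFT also has force. A reader might infer that a repeat LFT excludes INR because the > 5 to ≤ 8 × ULN row asks for a repeat LFT and then lists PT/INR in the follow-up column. The documents do not support that step: the same list also itemises ALT, AST, TBL and ALP, which an LFT plainly contains. What can be said is that no text names INR for this band and that the content of LFT is not defined.

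A last objection is that a required INR would force an anticoagulated patient with a mild ALT rise off treatment. Table 8-1 exempts known bone pathology (for ALP) and Gilbert syndrome (for TBL) but gives the INR criterion no exemption, and Tables 5-1 and 5-2 do not list anticoagulants as prohibited. This is a fair point, and the fix has to deal with it.

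**Conclusion.** The point holds for one band. In asymptomatic patients with ALT or AST > 3 to ≤ 5 × ULN, finding a mandatory stopping event depends on a discretionary test, unless the laboratory manual or the site's own LFT panel includes INR. Discontinuation itself is not discretionary once an INR > 1.5 is known; only ordering the test is.

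A reader might infer that the criterion cannot be applied anywhere, or that many doses would be given in error. Neither follows. At > 5 to ≤ 8 × ULN the follow-up list already includes PT/INR. Any count of doses at risk would describe a single hypothetical patient with assumed result dates, since the documents give no event rate.

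Few if any patients are likely to be affected. No efficacy result, error rate or sample size changes, and the SAP needs no correction. This is an inexpensive patient-safety improvement, not a flaw that threatens the trial.

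**What to change.** 1. In Section 7.3 (laboratory trigger) and in the > 3 to ≤ 5 × ULN row of Table 8-2, require PT/INR from the same draw as the confirmatory repeat LFT. Section 7.3 already allows a local laboratory for the repeat; allow it for the INR too.
2. Qualify the INR criterion in Table 8-1, and the matching row of Table 8-2, with: *in the absence of anticoagulant therapy or another known cause of raised INR*. This follows the pattern of the exemptions already given for bone pathology and Gilbert syndrome.
3. Check the laboratory manual first. If it already adds an INR to the repeat, item 1 reduces to aligning the protocol text with it.

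The trigger and event tiers stay as they are. The cost is one extra coagulation tube in a few patients, at a draw that is already required, and a few lines of text. One limit remains: if ALT and AST have fallen to ≤ 3 × ULN at the repeat, the event is not met on that sample even if the INR is raised. A row for this event in SAP Section 6.4 would be optional alignment.

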Appendix 9: ICS Dose Level

Table 9-1 Low, Medium and High Daily Doses of Inhaled Glucocorticosteroids for Adults and Adolescents (12 years and older) (GINA 2016)

Drug	Total Daily Dose (microgram/day)		
	Low	Medium	High
Beclomethasone dipropionate – CFC*	200 - 500	> 500 - 1000	> 1000
Beclomethasone dipropionate – HFA	100 - 200	> 200 - 400	> 400
Budesonide – DPI	200 - 400	> 400 - 800	> 800
Ciclesonide – HFA	80 - 160	> 160 - 320	> 320
Fluticasone propionate – DPI	100 - 250	> 250 - 500	> 500
Fluticasone propionate – HFA	100 - 250	> 250-500	> 500
Mometasone furoate	110 - 220	> 220 - 440	≥ 440
Triamcinolone acetonide	400 - 1000	> 1000 - 2000	> 2000
Fluticasone Furoate - DPI**	N/A	100	200

CFC: chlorofluorocarbon propellant; DPI: dry powder inhaler; HFA: hydrofluoroalkane propellant *Beclomethasone dipropionate CFC is included only for comparison with older literature

^{**}As per Relvar SmPC

## Document History - Changes compared to previous final version

Date	Time point	Reason for update	Outcome for update	Section and title impacted (Current)
10-Mar-2017	Prior FPFV	to Creation of final version	N/A – First version	NA
11-Sep-2017	Before lock	DB Creation of amendment 1	Asthma exacerbation endpoints updated to be consistent with protocol amendment 1	Section 2.7.6 Asthma exacerbation
11-Sep-2017	Before lock	DB Creation of amendment 1	Baseline definition for few endpoints	Section 2.1.1.2 Baseline definition Section 2.7.3 Rescue medication
11-Sep-2017	Before lock	DB Creation of amendment 1	[REDACTED]	[REDACTED]
11-Sep-2017	Before lock	DB Creation of amendment 1	[REDACTED] summary statistics for predicted FEV1 excluded	Section 2.3.2 Patient demographics and baseline characteristics
05-Oct-2017	Before lock	DB Creation of amendment 1	Text updated	Section 2.5.4 Supportive and sensitivity analysis
05-Oct-2017	Before lock	DB Creation of amendment 1	Text updated to clarify the analyses to be performed	Section 2.7.1 Spirometry data other than the primary endpoint
05-Oct-2017	Before lock	DB Creation of amendment 1	Analyses, that will be performed slightly differently from protocol mentioned way, has been updated	Section 4 Change to protocol specified analyses
05-Oct-2017	Before lock	DB Creation of amendment 1	Updated criteria for Hy's law as per current guideline	Section 6.4 Laboratory parameter-direction of interest and definition of clinically notable values
16-Oct-2017	Before lock	DB Creation of amendment 1	Subgroup category '1-<1.5' has been removed from baseline ACQ-7. Subgroup category <60% and >=90% has been removed for % predicted FEV1	Section 2.2.1 Subgroup of interest
14-Nov-2017	Before lock	DB Creation of amendment 1	Analyses for ACQ-5 included	Section 2.7.2 Asthma control questionnaire (ACQ)
24-Nov-2017	Before lock	DB Creation of amendment 1	Exclusion flags for protocol deviations included	Section 6.7 Rule of exclusion criteria of analysis sets
24-Nov-2017	Before lock	DB Creation of amendment 1	Term 'study treatment' clarified	Section 2.1.1 General definitions
5-Dec-2017	Before lock	DB Creation of amendment 1	Sub-group analyses for adverse events of special interest removed except for age-group	Section 2.8.2.2 Adverse events of special interest
18-Apr-2018	Before lock	DB Creation of amendment 1	Removed analyses for medical history by status.	Section 2.3.2
18-Apr-2018	Before lock	DB Creation of amendment 1	Removed compliance analyses by inhaler.	Section 2.4.1

---

Date	Time point		Reason for update	Outcome for update	Section and title impacted (Current)
18-Apr-2018	Before lock	DB	Creation of amendment 1	Added clarification on imputation of missing ACQ-7 items.	Section 2.6.3
18-Apr-2018	Before lock	DB	Creation of amendment 1	Updated sample size and sample size calculation according to Protocol amendment.	Section 1.1 and 3
18-Apr-2018	Before lock	DB	Creation of amendment 1	Removed Sodium	Section 6.4
18-Apr-2018	Before lock	DB	Creation of amendment 1	Updated multiple imputation.	Section 2.5.4 and 6.6
8-May-2018	Before lock	DB	Creation of amendment 1	Removed shift tables by visit and time point.	Section 2.8.4 and 2.8.5
29-May-2018	Before lock	DB	Creation of amendment 1	Updated baseline definition of PEF and other eDiary data.	Section 2.1.1.2 and 2.7.3
29-May-2018	Before lock	DB	Creation of amendment 1	Analyses that will be reported outside of CSR, have been mentioned	Section 5
30-May-2018	Before lock	DB	Creation of amendment 1	Notable value for magnesium included	Section 6.4
31-Jul-2018	Before lock	DB	Creation of amendment 2	Subgroups for race combined..	Section 2.2.1
31-Jul-2018	Before lock	DB	Creation of amendment 2	Added further details to actions in case model fails to converge.	Section 2.5.2 and 6.6
30-Aug-2018	Before lock	DB	Creation of amendment 2	Changed notable criteria for Magnesium to SI unit	Section 6.4
28-Sep-18	Before lock	DB	Creation of amendment 2	Added exclusion of implausible spirometry values	Section 2.5.1
28-Sep-18	Before lock	DB	Creation of amendment 2	Added non-parametric test exploration in case of non-convergence or highly skewed data.	Section 2.7.3 and 2.7.5.
21-Dec-18	Before lock	DB	Creation of amendment 2	Updated major PDs.	Section 6.7
26-Dec-18	Before lock	DB	Creation of amendment 2	Shift tables for urinalysis parameters removed	Section 2.8.4

---

## List of abbreviations

ACQ	Asthma Control Questionnaire
AE	Adverse Event
ALT	Alanine Aminotransferase
ANCOVA	Analysis of Covariance
AST	Aspartate Aminotransferase
AQLQ	Asthma Quality of Life Questionnaire
b.i.d	twice a day
BMI	Body Mass Index
BUN	Blood Urea Nitrogen
CCV	Cardio-/Cerebro-vascular
CRF	Case Report/Record Form (paper or electronic)
DMC	Data Monitoring Committee
eDiary	Electronic Diary
ECG	Electrocardiogram
ER	Emergency Room
FAS	Full analysis set
FDA	Food and Drug Administration
FEV 1	Forced Expiratory Volume in 1 Second
FEF	Forced Expiratory Flow
FVC	Forced Vital Capacity
IgE	Immunoglobulin E
ICS	Inhaled Corticosteroid
LABA	Long Acting Beta-2 Agonist
LFT	Liver Function Test
MF	Mometasone Furoate
MedDRA	Medical Dictionary for Regulatory Activities
MMRM	Mixed Model for Repeated Measurements
o.d.	Once a day
PEF	Peak Expiratory Flow
PK	Pharmacokinetic
PPS	Per protocol set
QTc	Corrected QT interval
RAN	Randomized set
SAE	Serious Adverse Event
SAF	Safety analysis set
SCS	Systemic Corticosteroids
SOC	System Organ Class
SMQ	Standard MEDRA Query
TD	Study Treatment Discontinuation
TFL	Table Figure Listing

## 1 Introduction

This document contains details of the statistical methods that will be used in the phase III clinical trial CQVM149B2303. This study is designed to evaluate the efficacy and safety of QMF149 150/80 microgram o.d. delivered via Concept1 compared with MF 200 microgram o.d. delivered via Twisthaler® in patients with asthma as determined by pulmonary function testing and effects on asthma control.

Data will be analyzed according to Section 9 of the study protocol.

Important information is given in the following sections and details are provided, as applicable, in section 6: [Appendix](#).

